Cover letter:

Official project title:

Technological-based Personalized Care Intervention for Supporting Older People with Diabetes Mellitus

Funding source: HKNU R&D Fund

NCT number: HE-RD/2023/1.11

Document updated date: 12/09/2023

Document updated date: 12/09/2023

HONG KONG METROPOLITAN UNIVERSITY

Study protocol

[figure not shown]

Figure 1: A flow diagram of the study

1. Research methodology

Diabetes mellitus (DM) has been declared a growing public health threat. DM affects approximately 463 million people around the world (1). Regarding the World Health Organization (WHO), DM is defined as fasting glucose equal to or higher than 7.0 mmol/L or a glucose level equal to or higher than 11.1 mmol/L two hours after a meal. A1C reflects the average blood glucose control in the last 2 to 3 months. As stated by American Diabetes Association (ADA), the optimal A1C level should be less than 7%. The prediabetes stage defines as an A1C level between 5.7 and less than 6.5%. WHO calls upon to strengthen, share and disseminate standards and to support interventions for diabetes management, preventing and slowing the progression of complications of DM through population and individual approaches (2). DM affects about 8.4% of the total population in Hong Kong (1). DM virtually affects the physiology of every body system mainly due to metabolic disturbances caused by hyperglycemia (2, 3).

Individuals with diabetes can make a dramatic impact on the disease progression and complications via self-management, which includes activities and behaviors of an individual undertakes to control and manage his or her health conditions. Poor diabetes management frequently causes more issues, which ultimately result in prolonged hospital admissions, more frequent outpatient visits, and higher prescription expenses.

Common self-management behaviors for individuals with diabetes are blood sugar monitoring, adopting healthy eating, being physically active, compliance with medications and healthy coping skills with good knowledge. Participating in all these five care has been demonstrated to have a significant effect on the progression and development of diabetes for individuals, as all of these five factors are associated with improved glycemic control, reduced complications and enhanced quality of life.

Just-in-time adaptive intervention (JITAI) is an evidence-based intervention to help intervention designers design to provide behavior change at right type/amount of support needed at right time at individual level (4). Mobile technologies such as smart-phones, mobile apps and various sensors can be used to provide interventions whenever and wherever needed (5). The core component of adaptive intervention embraces decision points (point in time at which treatment decisions made), intervention options (types, sources and modes of support delivery), tailoring variables (information concerning the participant that is used to make treatment decisions) and decision rules (which intervention option to offer based on the tailoring variables) (6). JITAI facilitates intervention designers to offer support in a timely manner and help the participant maintaining healthy behaviors. JITAI have been used to develop different interventions including physical activity and dietary counselling (5), mental health (7), and harmful substances (8). In recent study, the authors used JITAI to improve physical activity in older adults with type II DM via a mobile application (9).

- and 2045: Results from the International Diabetes Federation Diabetes Atlas, 9th edition. *Diabetes Research and Clinical Practice*, 157, 107843.
2. World Health Organization. (2016). Global Report on Diabetes. In *World Health Organization* (Vol. 978). <https://doi.org/ISBN 978 92 4 156525 7>
 3. Centre for Health Protection. (2017). *Report of Population Health Survey 2014/2015*.
 4. Wang, L., & Miller, L. C. (2020). Just-in-the-Moment Adaptive Interventions (JITAI): A Meta-Analytical Review. *Health Communication*, 35(12), 1531–1544. <https://doi.org/10.1080/10410236.2019.1652388>
 5. Goldstein, S. P., Zhang, F., Klasnja, P., Hoover, A., Wing, R. R., & Thomas, J. G. (2021). Optimizing a Just-in-Time Adaptive Intervention to Improve Dietary Adherence in Behavioral Obesity Treatment: Protocol for a Microrandomized Trial. *JMIR Research Protocols*, 10(12). <https://doi.org/10.2196/33568>

Quantitative arm – Setting and Participants: A block randomization, single-blind design will be used. A two-arm RCT with equal allocation between the intervention and control groups (1:1) will be used; only the assessors will be blinded to the treatment assignment. Convenience sampling with fitting the inclusion criteria will be selected as subjects.

Potential participants will be screened for fasting blood glucose and health history at baseline assessment. The potential participants who meet the inclusion criteria will be asked to sign a consent form before participation in this study.

Inclusion and exclusion criteria

A total of 60 those who are aged 60 and above and meet the inclusion criteria will be asked to sign a consent form before participation in this study. The inclusion criteria are: (i) aged \geq 60 years old; (ii) patients diagnosed with Type II DM (iii) patients experienced hypo (histix < 4.0 mmol/L) or hyperglycemia (histix ≥ 16.0 mmol/L); & (iV) The Abbreviated Mental Test (AMT) ≥ 6 . The exclusion criteria are: (i) patient on dialysis; (ii) taking ascorbic acid > 500 mg daily or (Not recommended by manufacturer as result may be affected); (iii) taking salicylic acid ≥ 650 mg single dose or (Not recommended by manufacturer as result may be affected); or (iv) scheduled radiological therapy during CGM application (Not recommended by manufacturer as result may be affected).

Primary and secondary outcomes

The primary outcomes will be the point of care test (POCT) of HbA1C level and the secondary outcomes will be the fasting blood glucose, total cholesterol, blood pressure, anthropometric measurement, and Diabetes Self-Care activities questionnaire.

HbA1C level: The HbA1C will be measured by A1CNow system, which has been cleared by the Food and Drug Administration (FDA) and certified by National Glycohemoglobin Standardization Program.

Lipid and glucose panel: The POCT lipid panel includes total cholesterol and blood glucose will be measured by CardioChek, which has been cleared by the Food and Drug Administration (FDA) and certified by the Centers for Disease Control and Prevention, Cholesterol Reference Method Laboratory Network (CRMLN).

Basic anthropometric measurement: The basic anthropometric measurement includes height, weight and body mass index.

Blood pressure: blood pressure will be measured by blood pressure monitors (Omron M7, Intelli IT, Kyoto, Japan) for assessment of brachial blood pressure.

Breath and blood Ketone: breath and blood ketone will be used to detect the presence of ketones in the breath and blood as indicators of hyperglycemia or diabetic ketoacidosis in individuals with diabetes.

Summary of Diabetes Self-Care Activities (SDSCA) Chinese version: To assess participants' diabetes self-care activities. The SDSCA will generate scores for five subscales: i) general diet, ii) eating a diet high in fruits/vegetables and low in high-fat foods, iii) daily activity, non-leisure and leisure activity, using three categories namely 'most active', 'moderately active' and 'least active', iv) taking recommended medications, v) glucose self-monitoring. Scores will be calculated on a continuous scale from 0-7, with the numerical value for each item based on the number of days during the week that the behavior was practiced. The item scores will then be averaged to derive an overall score for each self-care activity. The internal

reliability of the SDSCA is robust, acceptable reliability (0.55–0.64), with Cronbach's alphas 0.7.

Demographic and other covariates

Apart from gathering socio-demographic information such as age, marital status, gender, family income and education attainment, we will obtain data from the participants regarding their physical activity level, alcohol consumption, self-reported medical diagnosis, current medication usage and family history of first-degree relatives.

Statistical analysis

The statistical analysis will be performed using SPSS (Version: 26, SPSS Inc, Chicago). The alpha level will be set at 0.05 for two-tailed tests. One way analysis of variance model (ANOVA) will be used to compare the post-treatment scores over two time points.

Interventions: Non-invasive blood glucose monitoring

Non-invasive wearable glucose monitoring device will be used to capture participants' blood glucose. This device is non-invasive with no consumables, which used to check for participants' compliance with blood glucose monitoring and trend of blood glucose.

The arrangement of the intervention will be (1) training for self-management of DM and phone consultation; (2) phone call (or WhatsApp) follow up of hypo-or hyper-glycemic situations; (3) using sensor data to guide personalized care intervention. We will monitor the health data collected by this device regularly. A mobile application will be uploaded and recorded to monitor their compliance with the blood glucose monitoring.

Control group: Traditional self-monitoring of blood glucose

A control group with traditional self-monitoring of blood glucose will be used. The arrangement of the control group will be (1) training for self-management of DM and phone consultation; (2) phone call (or WhatsApp) follow up; (3) traditional self-monitoring of blood glucose will be used to guide personalized care intervention. The control group will be used as a comparative group to assess the effect of the non-invasive device in blood glucose monitoring.

Trained research assistant will keep close contact with all 60 participants through the scheduled regular phone calls or WhatsApp messages to understand their compliance and commitment to the monitoring of blood glucose. Analysis will be done to evaluate the effectiveness of the non-invasive wearable blood glucose monitoring device.

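### A control participant may keep using a personal glucose sensor, because the plan neither excludes nor records this, so the device effect may be diluted by an unknown amount.

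*Combined protocol and SAP*

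**What the plan says.** The section on the control group states: "A control group with traditional self-monitoring of blood glucose will be used". It gives the reason for having that group: "to assess the effect of the non-invasive device in blood glucose monitoring". Both arms receive diabetes self-management training, phone consultation and follow-up by call or message. The main planned difference is what guides the personalised care: sensor data in arm 1, traditional readings in arm 2. Arm 1 follow-up is also tied to low and high glucose episodes.

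The section on inclusion and exclusion criteria asks for age, Type II diabetes, an experienced low or high reading, and a minimum mental test score. The exclusions begin "The exclusion criteria are: (i) patient on dialysis" and go on to ascorbic acid, salicylic acid and scheduled radiological therapy. The last three cite the manufacturer and protect the accuracy of the reading. The radiological item mentions CGM application, but it concerns the therapy, not a person's own earlier or parallel use of a sensor.

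The primary outcome is HbA1c: "The primary outcomes will be the point of care test (POCT) of HbA1C level". It is measured at T0 and again after 8 weeks. Only assessors are blinded. The list of demographic and other covariates covers diagnoses, medication and habits, but not sensor use.

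**The concern.** The trial can estimate a device effect only if arm 2 does not have the device or something like it. As the criteria stand, a site would correctly enrol someone who already wears a personal sensor, and nothing tells that person what to do with it if allocated to control. If they keep it, they monitor in much the same way as arm 1.

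This cannot be repaired at analysis. Sensor use is not a listed data item, so a small or null HbA1c difference could mean that the device does little, or that the arms differed less than planned. The two could not be told apart.

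**Working it through.** **Step 1. Does any text close the gap?**

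| Place in the document | What it covers | Own-sensor use addressed? |
|---|---|---|
| Inclusion criteria (4) | age, diagnosis, low or high reading, mental test | No |
| Exclusion criteria (4) | dialysis, two substances, radiological therapy | No |
| Screening | fasting glucose, health history | Not named |
| Covariates | demographics, habits, diagnoses, medication, family history | No |
| Intervention section | study device, training, calls, app | No |
| Control section | traditional monitoring, training, calls | Not barred, not recorded |
| Regular calls to all 60 | compliance with glucose monitoring | Not named |

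The gap is open throughout.

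**Step 2. Size of the dilution.** Let d be the true difference between sensor-guided and traditional monitoring, and f the share of participants who would monitor by sensor whichever arm they are in. Simple case: a control participant with a personal sensor does as well as an arm 1 participant. Then the arm 2 mean shifts by f × d toward arm 1, and

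estimated effect = d × (1 − f).

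The documents give no f, so these values are assumptions.

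| f | People of 60 (60 × f) | Share of true effect (1 − f) |
|---|---|---|
| 5% | 3 | 0.95 |
| 10% | 6 | 0.90 |
| 20% | 12 | 0.80 |

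This assumes the whole contrast is lost. If a personal sensor removed only half of it, the factor would be 1 − 0.5f: 0.975, 0.95 and 0.90.

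**Step 3. What that means at this sample size.** Inputs from the plan: "A total of 60 those who are aged 60 and above and meet the inclusion criteria will be asked to sign a consent form"; "A two-arm RCT with equal allocation between the intervention and control groups (1:1) will be used"; "The alpha level will be set at 0.05 for two-tailed tests". So there are 60 / 2 = 30 per arm. The plan states no power, effect size, standard deviation (SD) or dropout, so it has no power calculation to reproduce, and SD units are used here.

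Detectable difference at 80% power with no dilution, normal approximation:

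(1.96 + 0.84) × √(2/30) = 0.72 SD (0.74 SD by the t distribution).

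With dilution, the true difference must be 0.72 / (1 − f), and the sample needed to keep the same power grows by 1 / (1 − f)².

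| f | Detectable true difference | Power if true d = 0.72 SD | Power if true d = 0.5 SD | Sample size factor |
|---|---|---|---|---|
| 0 | 0.72 SD | 80% | 49.1% | 1.00 |
| 5% | 0.76 SD | 75.9% | 45.2% | 1.11 |
| 10% | 0.80 SD | 71.3% | 41.4% | 1.23 |
| 20% | 0.90 SD | 61.1% | 34.1% | 1.56 |

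Exact t calculations give powers up to 1.5 points lower. The absence of a basis for 60 is a separate matter and does not decide this point.

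**Step 4. Why recent use matters as well as current use.** The opening section says A1C reflects control over the last 2 to 3 months. T1 comes 8 × 7 = 56 days after T0, which is slightly less than that window. Sensor use shortly before T0 is therefore reflected in the T0 value and may be partly reflected at T1. A 3-month look-back covers the longer end of the plan's own window.

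**The case against.** The best case against is that the documents show only that such people may enter, not that any will. That stands: no rate is given, and f may be close to zero.

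Nor does a prior user necessarily lose the contrast. Arm 2 is defined as traditional self-monitoring, so someone who stops a personal sensor on allocation keeps the contrast, and stopping could even widen the difference. Even a control participant who keeps a sensor is meant to have care guided by traditional readings, so some contrast may remain. All this stands, and it makes the (1 − f) figures a worst case for a given share of prior users. The main threat is continued use in arm 2.

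Channels for finding out already exist: health history at screening and regular calls to all participants. That also stands, but neither is told to ask about sensors.

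Three stronger readings are tempting and are not supported.

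- A reader might infer that the entry rule, by requiring a low or high reading, selects people likely to have been given a sensor before. Nothing in the documents says so. The criterion is a finger-prick type reading, and recruitment is by flyers in community centres.
- A reader might infer that people unable to run the app would miss the intervention or drop out, in arm 1 only. The plan gives the app one role: "A mobile application will be uploaded and recorded to monitor their compliance with the blood glucose monitoring". It does not say whose phone the app runs on or who operates it, and follow-up may be by ordinary phone call. This needs clarifying, but is not a shown error.
- A reader might therefore multiply a second loss for app inability onto the first. Without support for that loss, the product has no basis.

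**Conclusion.** The point holds in a limited form. The criteria do not exclude current or planned use of a participant's own glucose sensor, and nothing bars or records it in arm 2. The device effect may be diluted toward zero by an unknown amount that the planned data could not reveal. It would go too far to say that the effect is diluted.

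Under assumed shares of 5%, 10% and 20% without contrast, the effect would be about 0.95, 0.90 and 0.80 of its true size. This rests on two assumptions: that a personal sensor works about as well as the study device, and that those participants lose the whole contrast. This is a cheap improvement to make before enrolment, not a flaw that invalidates the design.

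**What to change.** 1. In the inclusion and exclusion criteria, add an exclusion applied to everyone before randomisation: current or recent use of a CGM or other glucose wearable (for example within 3 months of T0, matching the plan's own HbA1c window), or planned non-study use during the 8 weeks.
2. On the existing regular calls and at T1, ask all participants in both arms about non-study sensor use, and report the number by arm.
3. As a clarification only, state who supplies the phone and who runs the app.

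An app-ability requirement or a demonstration reading before allocation is not recommended. The first would narrow the population for reasons the documents do not establish, and the second would expose future controls to the device.

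Cost: one screening item and one question on calls that are already planned. A few people would be screened out, and the result would apply to older people not recently using a sensor, which the report should state. The 3-month window deals with carry-over in HbA1c; it does not bound habits learned from earlier sensor use.
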